### 3.3. SECONDARY OBJECTIVES AND OUTCOME MEASURES

Different secondary objectives are planned in this study with corresponding outcome measures:

#### 3.3.1.Time lapse needed in the management of mTBI in the ED:

- a)From TBI to VIDAS TBI result.
- b)From admission to VIDAS TBI result available for physician.
- c)From TBI to CT and from admission to CT.
- d)General management of TBI in the ER.

Outcome measures will be time to achieve each these steps in management, obtained directly from the Hospital's information and data systems.

#### 3.3.2.Direct costs consumption will be obtained from each ER episode of included patients and compared to age-matched historical controls (patients managed in Hospital 12 de Octubre for mTBI in the previous six months before implementation of the new protocol).

#### 3.3.3.Assessment of the proportion of cases being managed following the proposed algorithm

## 4. STUDY DESIGN

### 4.1. STUDY OVERVIEW AND STUDY POPULATION

This is a single center study with prospective data collection with a control reference group.

Patients to be included in the new clinical pathway:

-Adult Patients ( $\geq 18$  years of age) suffering mild TBI:( Defined by at least criterion a) and e) and one or more of the other criteria)

## BRAIN12-IMPLEMENTATION STUDY

- a) The presence of a plausible traumatic mechanism as described by the patient's recount of the injury event.
- b) Presence of one or more clinical signs attributable to brain injury: Loss of consciousness immediately following injury, alteration of mental status immediately following the injury, posttraumatic amnesia or any neurological abnormality.
- c) At least two acute symptoms related to the injury: feeling confused or disoriented, headache, nausea, vomiting, dizziness, vision problems, memory problems, emotional lability or irritability.
- e) GCS between 15 and 13, assessed at least 30 minutes after injury.

-Blood sample obtained ≤12 h after injury and before any imaging prescription.

Patients will not be included in the new pathway if:

- GCS 3-12 on admission
- Time of injury unknown
- Time to injury exceeding 12 hours
- Primary admission for non-traumatic neurological disorder (e.g., stroke, spontaneous, intracranial hematoma)
- Penetrating head trauma
- Patient with mechanical ventilation from the trauma scene or prehospital management.
- Venipuncture not feasible

Participation in the study will not affect patient management.

[figure not shown]

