1. STUDY SUMMARY

TITLE	Blood Biomarkers to improve management of mild traumatic BRAIN Injury implementation study
RUNNING TITTLE	BRAINI2 Implementation study
GENERAL OBJECTIVE	To assess the applicability and added value of a new clinical management pathway for patients with mild TBI presenting to the emergency department (ER), including the use of an in vitro diagnostic assay measuring the biomarkers GFAP and UCH-L1 in the serum, within the first 12 hours post-injury, to rule out the need for CT scan in mild TBI patients.
PRINCIPAL OBJECTIVE	
 
1) To evaluate the diagnostic performance of the VIDAS TBI (GFAP&UCH-L1) test in determining the need for CT-scan in patients with mild TBI admitted to the ER of Hospital 12 de Octubre.
 
2) To determine the safety of a management protocol including the use of the VIDAS GFAP&UCH-L1 test for patients with mTBI, in terms of complications or unforeseen neurological deterioration following the injury.
 
3) To estimate the reduction of CTs achieved using the biomarker test, by comparison with the management of TBI during the six months preceding the study (reference pathway).
 

PRINCIPAL OUTCOME	
Abnormal CT scan at admission in the ER
 
Deterioration: need for hospital admission or surgery due to TBI in the first week after TBI
 
Number of CTs prescribed in the management of mild TBI patients in the ER

PRINCIPAL OUTCOME MEASURES	
 
1) Diagnostic performance of the biomarker test
 
2) Proportion (%) of neurologic deterioration within 1 week post-TBI
 
3) Proportion (%) of CT scan prescribed in the ER over the period of the study for patients with mTBI
 

SECONDARY OBJECTIVES	
 
2.1) To determine the different times involved in the management of mild TBI patients and the effect of using the combined VIDAS test.
 
2.2) To establish differences in direct costs in the management of mild TBI in Hospital 12 de Octubre.
 
2.3.) To assess the compliance of physicians to the proposed algorithm.
 

SECONDARY OUTCOMES	
 
2.1) Time from admission to discharge. Time from admission to sample obtention. Time from venipuncture to availability of biomarker results.
 
2.2) Directs costs associated with mTBI management in the ER.
 
2.3.) Compliance with proposed algorithm.
 

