SECONDARY OUTCOME MEASURES	
 
2.1) Time differences with respect to reference group
 
2.2) Cost difference comparing before and after the implantation of the biomarker test.
 
2.3) Proportion (%) of cases in which management follow the proposed algorithm
 

METHODOLOGY	
The study will compare the different outcome measures between a historic group obtained 6 months before the initiation of the new management protocol and the group of patients admitted in the ER with a diagnosis of a mTBI after the initiation of the new bundle of care.
 
The combined GFAP&UCH-L1 test has been included in the new bundle of care of mTBI for the management in the ER of all patients with mTBI. In summary the test will be performed to all patients with mTBI admitted to the ER of Hospital 12 de Octubre and included in the new management pathway of patients with mTBI incorporated in our hospital. All patients suffering a mTBI(GCS 15-13) and admitted within 12 hours of the TBI will be included in this pathway. If the patient is included in this pathway, the prescription of cranial CT will be performed following the results of the VIDAS TBI test if the patient has had a significant TBI and a GCS of 14 or 15. Those patients with GCS of 13 or a focal neurological deficit will receive both biomarkers and CT for their management during the study period. The VIDAS TBI test interpretation as defined by the manufacturer, bioMérieux, takes into account the responses of the two biomarkers: the VIDAS TBI test is negative if the two markers GFAP and UCH-L1 are negative (below the previously defined threshold concentration for each of the biomarkers). The test is positive if at least one of the two GFAP or UCH-L1 biomarkers is positive (beyond the threshold concentration). This test is already CE marked and has already been tested on a large number of European patients and has demonstrated good safety and reliability profiles.

STUDY TYPE	Protocol evaluation Implementation Study
STUDY DESIGN	Implementation study with prospective data collection with a control reference historic group
STUDY POPULATION	Mild TBI patients with significant brain trauma admitted in the ER of Hospital 12 de Octubre

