#### 3.2. PRIMARY OBJECTIVE AND OUTCOME MEASURE

The primary objective of the study is to evaluate the performance of the two biomarkers GFAP and UCH-L1 assay to rule out the need for CT scan after mTBI.

The primary outcome will be the result of brain CT. Performance of the test will be analysed, as described in the assay instruction for use, to rule out the need for a CT scan after mTBI.

CT results will be obtained following the usual management pathway, using local radiologist report to determine the presence of pathological findings. Patients in whom no CT will be performed (i.e.: some GCS 15 without RF and GCS 14 with negative biomarkers test), will be ascribed as CT negative for the analysis if there is no deterioration or further evaluation that determines the need for a CT for other reasons.

Both GFAP and UCH-L1 biomarkers will be tested by two separate immunological assays using the usual clinical management and pathway in the management of mTBI. The positivity thresholds for each of the biomarkers and the two biomarkers' combination were validated by the company Banyan Biomarkers in an independent study, ALERT-TBI [13] and confirmed by bioMérieux using the VIDAS TBI with the same ALERT-TBI cohort and with the BRAINI study. The test will be performed if the patient is included in the new management pathway of patients with mTBI incorporated in our hospital. If the patient is included in this pathway, the prescription of cranial CT will be performed following the results of the VIDAS TBI test obtained. Patients with GCS of 13 will receive both biomarkers and CT scan for their management. Patients not following the clinical pathway (GCS<13 or non TBI patients) will be excluded from the study and managed according to routine clinical practice.

The VIDAS TBI test interpretation as defined by the manufacturer, bioMérieux, takes into account the responses of the two biomarkers: the VIDAS TBI test is negative if the two markers GFAP and UCH-L1 are negative (below the previously defined threshold concentration for each of the biomarkers). The test is positive if at least one of the two GFAP or UCH-L1 biomarkers is

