## 5.2. STUDY TIMELINE AND PLANNED MANAGEMENT ALGORITHM

All patients with TBI admitted to the ER and with a GCS between 13 and 15 will receive a blood test for biomarker determination upon admission. All patients with GCS of 13 or with a focal neurological deficit on admission will receive a CT. CTs could be performed to GCS14 and 15, independently of the result of the combined test, but the results of the test will be taken into consideration to guide for prescribing a CT. The attending physician will be responsible for the management of the patient and will have to determine the reason to prescribe CT despite normality of the biomarker test. The management algorithm that is recommended is as follows:

Risk factors (RF) include:

- Loss of consciousness.
- Posttraumatic amnesia (anterograde or retrograde).
- Advanced age (over 65)
- Antithrombotic treatment including platelet inhibitors.
- Difficulty in assessing level of consciousness: Cognitive impairment, intoxication.
- Persistent symptomatology: Repeated vomiting, persistent headache.
- High energy or High-risk mechanism: Falls over one's height, car accident, pedestrian involved in traffic accident, or accidents in which other there are other seriously injured patients.

Data will be collected directly from a specified structured form in the electronic health record of the patient. All data will be pseudonymised. Information regarding follow up will be recorded from the electronic health record regarding new contacts with the hospital or need of further assessment.

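### If physician compliance is computed in the study population, skipped or late tests and omitted CTs drop out of the count, and the status of a CT after a negative test is left open

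*Protocol*

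**What the plan says.** The study summary sets the objective, "To assess the compliance of physicians to the proposed algorithm", and its measure, "Proportion (%) of cases in which management follow the proposed algorithm". Section 3.3.3 repeats it: "Assessment of the proportion of cases being managed following the proposed algorithm". None of these places says which cases form the denominator.

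Section 5.2 opens the pathway with the test: "All patients with TBI admitted to the ER and with a GCS between 13 and 15 will receive a blood test". Section 8.1 makes sampling depend on the attending physician's clinical indication, so whether the test is done is part of physician behaviour.

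The same act is a condition of entry. Section 4.1 requires "Blood sample obtained ≤12 h after injury and before any imaging prescription". The summary's version of the criterion keeps the 12-hour limit but treats sampling before imaging only as an ideal. Section 6.1 excludes and replaces participants who violate an inclusion criterion. Its examples include no sample, a sample after 12 hours, and no CT where the design called for one.

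On the CT decision, section 3.2 (like the summary's methodology text) says that "the prescription of cranial CT will be performed following the results of the VIDAS TBI test obtained". Section 5.2 says that "CTs could be performed to GCS14 and 15, independently of the result of the combined test". The same sentence goes on to say that the result will guide the decision, and the next one asks the physician for a reason when a CT is ordered despite a normal test.

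**The concern.** A compliance proportion has to be able to record non-compliance. Here a physician who skips the test, or draws it too late, makes the patient ineligible. A physician who omits a required CT has the patient removed and replaced. Each is a plain departure from the algorithm, and each leaves the study before it can be scored. Of the main departures, the one that stays countable is a CT that the algorithm did not call for, and the protocol does not settle whether that is a departure.

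The background (section 2.1) argues that physicians do not follow existing CT decision rules and puts CTs outside those rules at up to 40%. Adoption is therefore a central question for an implementation study. A figure restricted to patients who were already tested would answer a narrower question than objective 2.3 asks.

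**Working it through.** **No stated figure.** The protocol gives no target, expected value or sample size for compliance, so there is nothing to reproduce on this point.

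**Step 1: which departures survive the entry and exclusion rules.**

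| Departure from the algorithm | Where the protocol sends the patient |
|---|---|
| No sample drawn | Not eligible (summary, 4.1); excluded and replaced (6.1) |
| Sample after 12 hours | Not eligible (summary, 4.1); excluded and replaced (6.1) |
| Required CT omitted | Excluded and replaced (6.1) |
| CT ordered before the sample | Out under 4.1; in under the summary |
| CT after a negative test, GCS 14 to 15 | In; scoring not stated (3.2 against 5.2) |

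The first three rows hold under either version of the sampling criterion. Only the fourth depends on which version governs.

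**Step 2: effect on the proportion.** Let s be the share of otherwise eligible patients kept in the study population, and c the compliance among those kept. Patients dropped for one of the first three reasons are non-compliant by definition, so

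compliance over all eligible = s × c + (1 − s) × 0 = s × c.

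The study population yields c. The ratio of reported to all-eligible compliance is c / (s × c) = 1/s. It is at least 1, and equals 1 only if nobody is dropped.

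The protocol gives neither s nor c. Both are assumptions here, with c = 80%:

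| s | Factor 1/s | Reported | All eligible (s × c) |
|---|---|---|---|
| 95% | 1.05 | 80% | 76% |
| 90% | 1.11 | 80% | 72% |
| 80% | 1.25 | 80% | 64% |

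**Step 3: CT after a negative test.** Let q be the share of sampled patients who test negative and r the share of those who still get a CT. Taking this as the only departure, compliance among the sampled is 1 − q × r if such a CT counts against the algorithm, and 100% if it does not. For assumed q of 20% to 50% and r of 10% to 40%:

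- smallest effect: 1 − 0.20 × 0.10 = 98%;
- largest effect: 1 − 0.50 × 0.40 = 80%.

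The scoring choice alone thus moves the result by 2 to 20 points over these ranges. This is an ambiguity: it raises the figure only if such CTs are scored as compliant.

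**The case against.** The strongest reply is that no text limits the compliance denominator to sampled patients. Section 5.3.3 finds the mTBI cohort by a unified diagnosis code and a form, not by the sample, and transfers data on mTBI patients from both periods into the database. A statistical analysis plan could name the wider denominator. This stands as far as it goes: the documents do not say that compliance is measured only in tested patients, so the bias is conditional. But entry and exclusion are protocol rules, and an analysis of the included cohort would inherit them unless the protocol says otherwise.

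A reader might infer from section 5.2 that almost no CT decision in GCS 14 to 15 could be non-compliant, and that the figure is inflated by construction. The full text does not support this. It describes a recommended algorithm, room for the physician to override it, and a reason to be given. A permitted override need not count as following the algorithm. The section 5.3.3 dashboard also shows the percentage of CTs requested in biomarker-negative patients, so overrides will be visible. What stands is that the scoring is not fixed. The algorithm figure and Appendix 1 are not available here and may bear on it.

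A reader might also set the roughly 1000 patients to be tested against the yearly volumes of 3000 (summary) and 3500 (section 7.1). That gives 1000/1500 = 66.7% and 1000/1750 = 57.1% per half-year. These are not estimates of s. The 3500 are suspected TBI taken from discharge codes, and neither volume is stated to have the eligibility criteria applied. The summary expects around 1000 patients to be triaged for mild TBI in the six months, the same number that section 7.1 expects to test. The gap is not evidence of untested eligible patients.

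Finally, objective 2.3 is secondary and has no target or decision attached. That limits the consequence but does not remove the defect.

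**Conclusion.** The point holds in a conditional form. If objective 2.3 is analysed in the population defined by sections 4.1 and 6.1, missing samples, late samples and omitted required CTs cannot be counted. Reported compliance then exceeds compliance over all eligible patients by a factor 1/s. The direction follows from the protocol's own rules; the size cannot be derived from it. The factors of 1.05, 1.11 and 1.25 rest on assumed s of 95%, 90% and 80%.

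Two inconsistencies add to this. The summary and section 4.1 differ on whether a patient whose CT was ordered first is eligible. Section 3.2 and section 5.2 leave open how a CT after a negative test is scored. Neither adds a proven upward bias, but both must be reconciled before the proportion has a fixed meaning. The diagnostic performance analysis is not touched by this point.

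**What to change.** For objective 2.3 only:

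- **Denominator.** Use all ER patients found by the mTBI code and form (section 5.3.3) who meet the clinical inclusion criteria and the exclusions, leaving out the blood-sample criterion. Late arrival, unknown time of injury and infeasible venipuncture remain reasons to be outside it.
- **Section 6.1.** State that exclusion and replacement do not apply to this objective. Without this, the wider denominator would conflict with the protocol.
- **Scoring.** Count a missing sample, a late sample, and an omitted CT that the algorithm called for as departures.
- **Reconciliation.** Align the summary with section 4.1 on the order of sample and imaging. Align the summary's methodology text and section 3.2 with section 5.2 on how a CT after a negative test is scored. Report such CTs as their own category with the recorded reason, so that the result can be read under either scoring. This concerns counting only and leaves physicians' discretion as it is.

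Keep the sampled cohort for diagnostic performance. The cost is protocol wording and one wider query of the electronic record, with no added patient contact. The reported compliance figure may be lower.

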INCLUSION CRITERIA	
-All adult patients suffering mild TBI:( Defined by at least criterion a) and d) and one or more of the other criteria)
 
    a) The presence of a plausible traumatic mechanism observed/or related by the patient's recount of the injury event.
 
    b) Presence of one or more clinical signs attributable to brain injury: Loss of consciousness immediately following injury, alteration of mental status immediately following the injury, posttraumatic amnesia or any neurological abnormality.
 
    c) At least two acute symptoms related to the injury: feeling confused or disoriented, headache, nausea, vomiting, dizziness, vision problems, memory problems, emotional lability or irritability.
 
    d) a GCS between 15 and 13, at least 30 minutes after injury.
 
-Blood sample obtained ≤12 h after injury and ideally before any imaging prescription.

EXCLUSION CRITERIA	
 
· GCS 3-12 on admission
 
· Age Below 18 years
 
· Time of injury unknown
 
· Time to injury exceeding 12 hours
 

BRAINI2-IMPLEMENTATION STUDY

	
 
· Primary admission for non-traumatic neurological disorder (e.g., stroke, spontaneous, intracranial hematoma)
 
· Penetrating head trauma
 
· Patient with mechanical ventilation from the trauma scene or prehospital management
 
· Venipuncture not feasible
 

NUMBER OF SUBJECTS	The implementation study will last for 6 months. The number of patients that are normally treated for this pathology is around 3000 patients each year. During the 6 months of the study around 1000 patients will at least be triaged for mild TBI
STUDY CENTRES	Hospital 12 de Octubre
PROVISIONAL CALENDAR OF THE STUDY	
 
- Start of inclusions: Jan 2025
 
- Inclusion period: 6 months
 
- End of inclusions: July 2025
 
- Length of participation of each subject: 2 weeks
 
- Total length of the study: 6 months
 

STATISTICAL ANALYSIS	
Outcome assessment
 
CT scan status will be attributed to each study participant based on the presence of intracranial lesions. Local CT reading will be used.
 
Outcome assessors will be blind to the participant biomarker status.
 
Quality control outcome assessment will be performed over the study period via sequential intra/inter observer agreement assessment.

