## 6. STUDY STOPPING RULES

### 6.1. STUDY STOPPING CRITERIA FOR A PARTICIPATING SUBJECT

Participants will be excluded from the study and replaced in case of a violation of an inclusion criterion, e.g. in the mTBI group: no mild TBI, no CT scan when the patient should have received one according to the study design, no blood sampling or after 12 hours post-injury.

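### Section 4.1 makes sampling before any imaging request mandatory, the summary makes it a preference, and Section 6.1 could turn the difference into exclusion of CT-first patients

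*Protocol*

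**What the plan says.** The same criterion appears twice in the current protocol.

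- Study Summary, inclusion criteria: "Blood sample obtained ≤12 h after injury and ideally before any imaging prescription".
- Section 4.1, patients to be included in the new pathway: "Blood sample obtained ≤12 h after injury and before any imaging prescription".

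Section 6.1 gives the consequence of failing a criterion: "Participants will be excluded from the study and replaced in case of a violation of an inclusion criterion". Its examples are introduced as examples only. Those on sampling are "no blood sampling or after 12 hours post-injury"; the order of sample and CT request is not among them.

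Three further statements decide why this matters. Section 3.2 sets the reference standard, "The primary outcome will be the result of brain CT". Within the pathway, "the prescription of cranial CT will be performed following the results of the VIDAS TBI test obtained". Patients who are not scanned "will be ascribed as CT negative for the analysis if there is no deterioration", and if no later evaluation calls for a CT. Section 3.2 also compares the number and proportion of patients scanned with patients seen in the previous six months, and Section 3.3.3 measures the proportion managed according to the algorithm.

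**The concern.** A patient sampled in time, but after the CT was requested, meets the summary criterion and fails the one in Section 4.1. If Section 6.1 is applied to the Section 4.1 list, that patient leaves the study. Two teams working from this protocol could therefore analyse different cohorts.

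The affected patients matter for two results.

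**Accuracy.** A CT requested before the sample was not selected by the test result. If it is carried out, a lesion missed by the test is found. In a test-negative patient who is not scanned, the same lesion is counted as CT negative unless it surfaces later. Removing CT-first patients shifts the analysis towards the second situation.

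**CT use and compliance.** CT-first patients are mostly scanned, and those at GCS 14 or 15 without a focal deficit are often departures from test-guided ordering. The historical group has no sample-order criterion. Dropping these patients from the new period alone lowers its scan proportion and raises its compliance proportion.

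**Working it through.** **1. The texts side by side**

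| Patient sampled within 12 h | Study Summary | Section 4.1 with Section 6.1, read strictly |
|---|---|---|
| Sample before CT request | included | included |
| Sample after CT request | included | criterion violated; excluded and replaced |

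The conflict is textual and depends on no figure.

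**2. The plan's own figures (Section 7.1)**

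1000 × 0.10 = 100 CT positives, as stated. The target of a lower 95% limit for NPV of at least 97.0% can be neither confirmed nor refuted, because the protocol gives no expected sensitivity, specificity or NPV. The target can turn on one case. At an assumed specificity of 30%, 2 false negatives among 272 test-negatives give an exact lower limit of 97.4% (met), and 3 among 273 give 96.8% (not met).

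**3. Effect on accuracy**

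Assumptions, none from the protocol: true sensitivity 97%, specificity 30%, CT-first share f of 10, 20 or 30%, and the same 10% prevalence in both groups. All CT-first requests are carried out. No test-negative patient is scanned in the test-first group, and 30% of missed lesions there surface later.

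Per 1000 patients: true positives 97, missed lesions 3, true negatives 900 × 0.30 = 270, test-negatives 273, true NPV 270/273 = 98.9%.

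- CT-first patients kept: missed lesions seen = 3f + 0.30 × 3(1 − f).
- CT-first patients excluded and replaced: missed lesions seen = 0.30 × 3 = 0.90.
- Apparent sensitivity = 97/(97 + seen); apparent NPV = (273 − seen)/273.

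| f | Seen, kept | Sensitivity, kept | NPV, kept | Sensitivity, excluded | NPV, excluded |
|---|---|---|---|---|---|
| 10% | 1.11 | 98.9% | 99.6% | 99.1% | 99.7% |
| 20% | 1.32 | 98.7% | 99.5% | 99.1% | 99.7% |
| 30% | 1.53 | 98.4% | 99.4% | 99.1% | 99.7% |

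Exclusion is further from the truth (97% and 98.9%) in every row. The gap depends on the assumptions:

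- If all missed lesions surface, both wordings give 97% and 98.9% and the gap is zero.
- If 30% of test-negatives are also scanned by override, at f = 10% sensitivity is 98.3% kept and 98.45% excluded.
- If no missed lesion surfaces and f = 30%, 0.9 are seen when kept: 97/97.9 = 99.1%, against 100% when excluded.

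**4. A higher lesion rate among CT-first patients**

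Assume 10% CT-first with 30% CT positive, sensitivity 96%, and 25% of misses surfacing in the other group. CT-first patients give 30 × 0.04 = 1.2 false negatives, all seen if scanned. The others give 70 × 0.04 = 2.8, of which 0.7 are seen.

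- Kept: 96/(96 + 1.9) = 98.1%.
- Excluded: 67.2/(67.2 + 0.7) = 99.0%.

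The bias is 2.1 points when these patients are kept and 3.0 when they are excluded, so most of it remains after the change.

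**5. Effect on the scan proportion**

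Under the assumptions of step 3, test-positives are 97 + 900 × 0.70 = 727 per 1000, so 72.7% of test-first patients are scanned. Keeping CT-first patients gives f + (1 − f) × 0.727 = 75.4, 78.2 and 80.9% for f = 10, 20 and 30%. Excluding them gives 72.7% throughout. The scan proportion is understated by f × 0.273, or 2.7, 5.5 and 8.2 points. Test-independent CTs in the test-first group, or cancelled requests in the CT-first group, make this smaller.

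**The case against.** Several points on the other side stand.

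- **Exclusion for order is inferred.** Section 6.1 does not list it. The list labelled as inclusion criteria is the one in the summary, while Section 4.1 describes entry to the pathway. A reader might infer that the protocol already orders CT-first patients out; it only permits that reading.
- **Who is affected is unknown.** A reader might infer that the strict wording falls hardest on patients with GCS 13 or a focal deficit, since "All patients with GCS of 13 or with a focal neurological deficit on admission will receive a CT". But Section 5.2 has blood drawn on admission for everyone with GCS 13 to 15, and those sampled before the request stay in under either wording.
- **Requested is not scanned.** A CT requested first could be cancelled after a negative result. It is too strong to say that a false negative in this group is always seen.
- **The strict rule has some purpose.** If the scan comes first, its result may influence whether blood is then drawn, and patients without a sample are excluded. CT-first patients who do have a sample may be selected on the outcome. A strict order also isolates test-guided requests.
- **Replacement.** Section 6.1 replaces excluded patients, so a fall in CT positives such as from 100 to 70 assumes that no replacement takes place.

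These points limit the size of the problem and call for a sensitivity analysis. They do not remove the conflict between the two wordings.

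**Conclusion.** The point holds as an unreconciled eligibility criterion with a foreseeable direction of bias. Applying Section 4.1 strictly through Section 6.1 would tend to raise apparent sensitivity and NPV, the apparent CT reduction and the compliance proportion.

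The number affected is not in the protocol, and every size above rests on assumed values. At a 10% CT-first share the accuracy shift is 0.2 points in sensitivity and 0.1 in NPV with equal prevalence, and 0.9 points in sensitivity if lesions are concentrated among CT-first patients. The scan proportion shifts by up to 2.7 points. All shrink towards zero if most patients are sampled on admission. The accuracy shift also shrinks if missed lesions usually surface, and both shrink if negative tests are often overridden.

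A reader might infer that the summary wording makes the accuracy estimate unbiased. It does not: the larger part comes from counting unscanned patients as CT negative in Section 3.2, which is a separate matter.

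**What to change.** - In Section 4.1, use the summary wording, so that sampling before the imaging request is a preference in both places.
- In Section 6.1, state that a CT requested before the sample is not by itself a reason for exclusion from the analysis.
- Keep these patients in the accuracy, CT-use and compliance analyses, and flag them.
- Report accuracy with and without them where request and sample times are available, because CT-first patients who were later sampled may be a selected group. The time outcomes listed in the summary and Section 3.3.1 cover sample, result and CT, but not the CT request, so its availability in the hospital systems should be confirmed.

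The cost is two sentences and one extra sensitivity table. Only who is analysed changes; patient care does not.
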